Study Procedure Study Day	-2 to 0 ⁵	0	7 ± 2	14 ± 2	21 ± 2	30 ± 3	60 ± 3 and every 30 ± 5 until resolution	after end of	treatment ²		
Screening/Administrative/Baseline											
Informed consent	X										
Parent(s), legal guardian(s), or legally authorized representative (LAR) Informed consent ⁶	X										
Demographics	X										
Review medical history ⁷	X										
Inclusion/exclusion criteria	X										
Clinical suspicion of an Acanthamoeba infection by typical clinical findings	X										
Confirmation of Acanthamoeba infection by confocal microscopy ⁸	Х										
Corneal scraping ⁹	X									x	
Vital signs 10	X										
Study Drug Administration			•	,							
Randomization 11		X									
Dispense study drug ¹²		х				X	X			x	
Study drug administration ¹³		Х	х	х	Х	Х	X			X	
Efficacy Assessments											
Best corrected visual acuity		\mathbf{x}^{11}									X
Slit lamp examination		\mathbf{x}^{11}	х	X	X	X	X	X	X	X	X
Pupil test (swinging light test) 14		\mathbf{x}^{11}	X	X	X	X	X	X	X	X	X

Visits ¹	Screening			Tre	atment	Period	Follow-	up Period	Relapse ³	End-of-study 4	
Study Procedure Study Day	-2 to 0 ⁵	0	7 ± 2	14 ± 2	21 ± 2	30 ± 3	60 ± 3 and every 30 ± 5 until resolution	after end of	treatment ²		
EQ-5D questionnaire 15,16		\mathbf{x}^{11}	X	X	X	X	X	X	X	X	X
Visual functioning questionnaire (VFQ25) 15,17		\mathbf{x}^{11}	X	X	X	X	X	X	X	X	X
Safety Assessments											
Hematology, biochemistry	X										x
Urinalysis (dipstick)	х										х
Urine pregnancy dipstick (women of childbearing potential only	Х					X	Х	х	X	X	х
Use of topical steroids and oral NSAIDs 18	X				Х						
IOP		\mathbf{x}^{11}	Х	х	Х	х	X	X	X	X	х
Ophthalmoscopy 19		\mathbf{x}^{11}									х
Photography of affected cornea		\mathbf{x}^{11}				х			X		х
Ongoing Subject Review											
Concomitant therapy ⁷	x	X	x	X	Х	X	X	x	X	X	х
Adverse events	х	Х	Х	х	X	X	X	х	X	X	х

- 1. During each visit, subjects will enter the clinical research center and will leave after completion of all assessments.
- 2. If subjects are cured 90 days after end-of-treatment visit, the study-end-point is reached and the End-of-Study assessments will be performed.

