3.1.3. Treatment Period

On Day 0, subjects will arrive at the clinical research center for the baseline assessments and will receive instructions on how to apply the eye drops. Subjects will be randomized to 1 of the 2 treatment groups.

Subjects will receive multiple doses of 0.08% PHMB + placebo or 0.02% PHMB + 0.1% propamidine combination therapy in the affected eye until resolution according to the treatment schedule presented in Section 5.2 Drug dosage and Administration.

On Day 0, the first application of study medication will be done at the research center after completion of all baseline assessments and randomization. Thereafter, subjects will leave the clinical research center and study drug will be self-administered at home. Subjects will return to the clinical research center for ambulant visits on Days 7, 14, 21, 30 and every 30 days until resolution.

Assessments will be performed during the treatment period as presented in the schedule of assessments.

Follow-up medical examinations will be performed 30 and 90 days after end of treatment. The specific procedures that will be performed are presented in the schedule of assessments.

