7.1.1 Presentation of Results

All results will be presented for each visit by treatment group and in total, unless stated otherwise. It should be clearly stated which unit applies to each presented variable.

Continuous data will be summarised using descriptive statistics, and the following parameters will be reported:

- number of subjects with evaluable observations and missing observations
- arithmetic mean and change from baseline with standard deviations

LINK Medical Study ID: PSR012

- median
- first and third quartiles
- minimum and maximum

Categorical data will be presented using absolute frequency and percentage. When the absolute frequency is zero, the percentage will not be presented. Unless stated otherwise, the denominator for percentage calculations will be the total number of subjects in the applicable analysis set, including subjects with missing data. For variables with missing values, the number and percentage of subjects with missing values will be presented.

Significance tests will be two-sided and performed at the 5% significance level, unless stated otherwise. When reporting the results of significance tests, p-values will be presented.

All confidence intervals (CIs) presented will be two-sided with a nominal confidence level of 95%, unless stated otherwise.

Data will be presented using an appropriate number of decimal places, to ensure that undue precision is not implied (e.g. the number of decimals should not exceed the accuracy of the measuring instrument). Raw data will be presented with the same number of decimals as collected, and derived data with an appropriate number of decimals based on general practice, mathematical rationale or scientific rationale.

Minimum and maximum values will be presented with the same number of decimals as the analysed variable and the other descriptive statistics will be presented with one decimal more. Percentages and proportions will be presented with one decimal. Odds ratios and hazard ratios will be presented with 3 decimals, and small and large values will be presented as '<0.001' and '>999.999' respectively. CI bounds will be presented with the same number of decimals as the corresponding point estimate, and p-values will be presented with 4 decimals or as '<0.001'.

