7.1.4 Analysis Visit

An analysis visit is defined as a categorical variable used to classify values within an analysis variable into temporal or conceptual groups used for analyses.

The visits as defined in the case report form, CRF, will be used as analysis visits. The Schedule of Assessments table provide acceptable deviations from the specified study day at which study visits should occur. These are \pm 2 days up to study day 22, called study day 21 in the Schedules table, ref. section 7.1.3 above, \pm 3 days from study day 31 to 30 days after end of treatment (EoT), and \pm 5 days at the 90 day after end of treatment visit. A review of assessment times will be conducted before the clean file meeting. Necessary revisions will be documented in the Clean file report. Results tables will present statistics by visit number. Where deemed necessary, longitudinal analyses will use the observed durations from baseline. The mean duration in days between visits will be presented.

Study day windows

Study visit day	Target study day of visit	Window of study day visit
0	0	± 0 days
7	7	± 2 days
14	14	± 2 days
21	21	± 2 days
30	30	± 3 days
60	60	± 3 days
30 days after previous visit§ until resolution	30 after previous visit	± 5 days
30 days after EoT	30 days after EoT	± 3 days
90 days after EoT	90 days after EoT	± 5 days

[§] The protocol states "and every 30 ± 5 days until resolution". This is interpreted as 30 days after the previous visit, and not a multiplicity of 30 days based on a fixed setup from baseline, i.e. not 31+60+n*30.

In general, data from unscheduled visits will be presented in data listings only and not included in analysis or summary tables. An exception to this is data used to confirm eligibility in association with screening or randomisation where the last assessment will be considered in summaries of screening data.

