The EQ-5D will be summarised for each dimension. A table presenting the number of subjects reporting a problem, i.e. a score higher than 1, will also be presented. A repeated measures ANCOVA for each dimension will be conducted using treatment and the baseline value as predictors.

The EQ VAS score, annotated as ORRES_EQ5D0206, is being recorded at all visits, including Baseline. Integer values range from 0 to 100. A repeated measures ANCOVA will be used to compare potential differences in trends over the treatment period using treatment and the Baseline VAS value as predictors.

Slit-Lamp Examination, at all visits

Below can be seen the different efficacy variables based on the Slit lamp examination. These will be presented in tables, as can be seen in the Data Display Plan (DDP). Some of these variables will only be recorded in *Specify* types of eCRF fields and will be converted to a *Yes/No* variable before tabulation and possible analysis.

Corneal scarring

Corneal scarring is being assessed as *Present* or *Absent*, using the slit lamp biomicroscopy, and is annotated as SLECOSCAR. This is being performed by the examining ophthalmologist, using a slit lamp biomicroscope. Detailed information about the procedure is provided in the Study Operation Manual. As a stated secondary variable, corneal scarring at EoT will be analysed with logistic regression using treatment group and corneal scarring at baseline as predictors.

Ulceration severity

Ulceration severity is being assessed as *Present* or *Absent* by the examining ophthalmologist using the slit lamp biomicroscope and is annotated as SLECOUL. As a stated secondary variable, ulceration severity will be analysed with logistic regression using treatment group and ulceration severity at Baseline as predictors.

Conjunctiva

Erythema grade SLECER (using grades 0, 1, 2, 3)

Oedema grade SLECED (using grades 0, 1, 2, 3, 4)

Discharge SLECOND (Present, Absent)

Papillae SLECONP (Present, Absent)

Follicles SLECONF (Present, Absent)

Limbitis

Scleritis

Corneal Abnormalities⁴

Dendritiform epithelial lesions

Perineural infiltrates

Corneal epithelial defects (punctate erosions),

Corneal epithelial ulcer (confluent erosions)

Corneal epithelial defects SLECOED (Present, Absent)

Corneal ulceration SLECOUL (Present, Absent)

Corneal epithelial opacity SLECOEO (Present, Absent)

Corneal stromal opacity SLECOSO (Present, Absent)

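### Monthly visits stop at resolution, so the planned repeated-measures comparison of EQ VAS over the treatment period understates any benefit from curing more subjects or curing them sooner

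*SAP*

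**What the plan says.** Protocol 3.1.3 sets the visits: "Subjects will return to the clinical research center for ambulant visits on Days 7, 14, 21, 30 and every 30 days until resolution". The Schedule of Assessments heads the monthly column "60 ± 3 and every 30 ± 5 until resolution". For cured subjects, "Follow-up medical examinations will be performed 30 and 90 days after end of treatment", and SAP 7.1.4 lists these as separate analysis visits timed from end of treatment ("30 days after EoT").

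SAP 7.9.3 says of EQ VAS: "A repeated measures ANCOVA will be used to compare potential differences in trends over the treatment period", with treatment and baseline VAS as predictors. Of the EQ-5D dimensions it says "A repeated measures ANCOVA for each dimension will be conducted using treatment and the baseline value as predictors", with no period stated. Neither sentence gives a time term, a covariance structure or a rule for missing data. SAP 7.1.5 defers missing-data handling to the variable-specific sections, and those contain none for these variables.

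SAP 7.9.3 tests corneal scarring at end of treatment, but gives no time point for the ulceration and anterior chamber models. SAP 7.1.4 adds: "Results tables will present statistics by visit number".

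Note 4 to the Schedule of Assessments defines End-of-study for subjects who complete the 90-day follow-up, who fail, who withdraw or who reach 12 months of treatment. The schedule marks EQ-5D, VFQ25 and slit lamp at that visit.

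**The concern.** A subject supplies treatment-period rows only up to and including the visit at which resolution is found. After Day 30, the monthly visits therefore over-represent slow responders, and the better arm loses more of its successes from them. That is selection after randomisation on the outcome the drug is meant to change. The subjects who stay unresolved longest also supply the most rows.

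The visits after end of treatment do not repair this within a treatment-period model, because they fall outside that period and run on a different clock. Relapse adds to the difficulty: under note 3 to the Schedule of Assessments, culture-negative relapsers restart at Day 0, so a visit number no longer fixes the time since randomisation.

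At stake is a report of little or no quality-of-life difference when one exists. These are secondary efficacy variables listed in the protocol, so such a statement would be read as a finding about the randomised groups.

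**Working it through.** The plan gives no quality-of-life figure to reproduce. Its own figure used here is the pair of cure rates behind the sample size (Protocol 7.6): 63% v 83%, two-sided alpha 0.10, 80% power, 10% loss.

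**1. Check of those rates.** n per arm = (1.645 + 0.842)² × (0.63×0.37 + 0.83×0.17) / 0.20² = 57.8, so 58 per arm. Then 58/0.9 gives 65 per arm, or 130. This matches the plan.

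**2. Assumptions that are not in the documents.** The resolution hazard is constant and set so that 63% and 83% resolve by Day 335 (12 months less the 30-day confirmation). EQ VAS rises by a fixed gap at cure, 20 points in the main case. Early treatment-failure exits are ignored.

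Daily hazard: control −ln(0.37)/335 = 0.00297; test −ln(0.17)/335 = 0.00529.

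**3. Attendance at a monthly visit** (not yet resolved at the previous one, 30 days earlier):

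| Visit | Control | Test |
|---|---|---|
| Day 90 | 84% | 73% |
| Day 180 | 64% | 45% |
| Day 300 | 45% | 24% |

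**4. Day-180 difference.**
- All randomised: the unresolved share is exp(−180h), 0.586 control and 0.386 test. The difference is 20 × (0.586 − 0.386) = 4.0 points.
- Attendees: the share resolving at that visit is 1 − exp(−30h), 0.085 control and 0.147 test. The difference is 20 × (0.147 − 0.085) = 1.2 points.

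The attendees show about 30% of the full difference. The gap cancels from that ratio: with a 10-point gap the figures are 0.6 v 2.0, and with a 30-point gap 1.8 v 6.0.

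**5. The model with the stated predictors (treatment and baseline), fitted across visits.**
- Everyone followed: the treatment coefficient is the average of 20 × [exp(−0.00297t) − exp(−0.00529t)] over Days 7, 14, 21, 30 and then every 30 days to 360. The 15 values are 0.32, 0.61, 0.89, 1.23, 2.18, 2.89, 3.41, 3.77, 4.00, 4.14, 4.19, 4.18, 4.12, 4.02 and 3.89. They sum to 43.84, and 43.84/15 = 2.9.
- Visits stopped at resolution, resolution visit included: 0.9 points. This comes from a random-intercept simulation with 58 per arm, 60 trials and assumed score variances; Monte Carlo SE 0.16. If sicker eyes are also slower to cure, it is 0.4.

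**6. End-of-study.** Expected difference 20 × (0.83 − 0.63) = 4.0; simulated 4.1.

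**7. Other specifications on the truncated visits.**
- Adding visit and treatment-by-visit terms gave 1.6 against 3.8 with full follow-up at Day 180 in one run, and 1.9 against 4.1 in another.
- A likelihood model with visit as a factor, from Day 30 on, with scores improving gradually over the 90 days before cure, gave 4.75 against 4.45 with full data (Monte Carlo SE about 0.3). That is no loss.
- A complete-case analysis would keep about 22 control and 10 test subjects of 58 per arm.

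**The case against.** The strongest reply is that the SAP is under-specified rather than wrong. Naming treatment and baseline as predictors does not exclude a within-subject time factor, and SAP 7.1.4 lets longitudinal analyses use observed durations from baseline where necessary. As the last step of the working shows, one likelihood model recovered the full effect. This stands in part. Whether the benefit survives depends on choices the SAP leaves open, and that is a reason to make them now. With only the stated predictors, most of the effect was lost when scores change at cure.

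Several stronger readings are tempting, and the documents do not support them:
- A reader might infer that these comparisons contain only uncured subjects. They do not: the resolution visit counts, and questionnaires and slit lamp are repeated at both follow-up visits and at End-of-study. The EQ-5D dimension model is not confined to the treatment period.
- A reader might extend the point to every secondary variable. Repeated-measures models are named only for EQ-5D and EQ VAS. VFQ-25 has scoring rules but no between-arm model. Ulceration and anterior chamber grade simply lack a time point.
- A reader might take the rule that "the denominator for percentage calculations will be the total number of subjects in the applicable analysis set" to mean that failures who left are tabulated as free of the sign. The same section requires the number and percentage missing to be shown, and SAP 7.3 tabulates attendance by visit. The percentage is diluted, but the absence is visible.

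The mock tables are in a separate Data Display Plan, so exact layouts cannot be checked.

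**Conclusion.** The point holds for EQ VAS as written, for the EQ-5D dimensions if they are modelled on treatment-period visits, and for by-visit tables after Day 30. Under the assumptions above, the stated model returns about 1 point where the same model with everyone followed would return about 3.

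A reader might set that 1 point against the End-of-study difference of about 4 and call the whole gap bias. That is not right: the End-of-study value is a different estimand, and the step from 3 to 4 arises because the model averages over early visits when few subjects are cured.

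The size rests on the assumed hazards, the 20-point gain, an abrupt change at cure and the model terms; more gradual improvement before resolution makes the loss smaller. In the Day-180 calculation, the proportion lost is the same whatever the gain.

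Importance is moderate. SAP 7.9.3 treats these analyses as hypothesis-generating, and CRR_12 and time-to-cure, which measure more and earlier cure directly, are untouched. The change should be made, but the primary conclusion does not turn on it.

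**What to change.** In SAP 7.9.3:
- Make the between-arm comparison of EQ VAS and the EQ-5D dimensions a baseline-adjusted ANCOVA at End-of-study, and add Day 30 as the fixed-time comparison, since visits up to then are fixed.
- Name the same End-of-study time point for the ulceration and anterior chamber models.
- Treat by-visit tables after Day 30 as descriptive, and show the number attending in each arm.
- If a repeated-measures model is kept, use days since randomisation, include the post-treatment follow-up and End-of-study visits, add time and treatment-by-time terms, and state the missing-data assumption. Adding time terms to the truncated visits alone is not reliably enough.

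The cost is SAP wording; the schedule already collects the data. The drawback is that End-of-study falls at different times from randomisation in cured and failed subjects, and the report must say so. Protocol 4.4 asks for End-of-study assessments at discontinuation only where possible, so the number missing at that visit should also be reported by arm.

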7.1.7 Multiplicity

Three hypotheses are specified in the Protocol, one primary and two secondary hypotheses. Time-to-resolution using the visit day at which resolution was first seen, will be considered statistically significant if the sum of the p-value for the primary variable and the p-value from the time-to-resolution analysis is less than the specified overall significant level. The use of a non-inferiority alternative if the difference alternative should not be obtained, does not affect the overall p-value level of the primary hypothesis.

Hypotheses tested for other secondary variables will all be analysed using significance elves of 0.05.

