7.9.3 Secondary Efficacy Variables¹

Time-to-cure comparison between the treatment groups is specified as efficacy hypothesis and will be subjected to formal statistical testing. Other analyses of secondary efficacy variables will be done on a hypothesis-generating basis, i.e. no p-value adjustments will be conducted, and conclusions regarding the analysis results will be commented on such a basis.

Time-to-cure

The aim of the hypothesis test is to show that the time is less among the subjects receiving PHBM 0.08% monotherapy compared to the comparator. Patients will either be classified as Cured at some point of time while in the study or leave the study without being classified as Cured. As a secondary efficacy variable, timeto-cure (clinical resolution) will be analysed. The Cox Proportional Hazards regression (subject to validity of the 'proportional hazards' assumption) and Kaplan-Meier survival plots. If the proportional hazard assumption is not fulfilled a logrank test will be performed. Not all patients may have information regarding when they were cured, e.g. due to death before being cured, or completed the study without being cured. Both the Cox Proportional Hazards regression and the Kaplan-Meier plot uses the censoring timepoint in their calculations. The censoring timepoint will be defined based on the timepoint of the last observation when cure status was assessed. The null hypothesis is that the two treatment arms have equal hazard functions. Relevant data will be presented at the Clean file meeting for discussion and acceptance.

BCVA

The VAMS states that: "Depending on the problem, this notation can be most useful when analysing or graphically plotting visual acuity scores because equal linear steps on the LogMAR scale represent equal ratios in the standard size sequence." Hence, BCVA will be presented and analysed using LogMAR values, where

$$LogMAR = \log \left(\frac{ORRES_{BCA2}}{ORRES_{BCA1}} \right),$$

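### The EQ VAS analysis is meant to compare trends between arms, but the listed predictors contain no time or treatment-by-time term, so as written the treatment test compares average level

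*SAP*

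**What the plan says.** In SAP 7.9.3 (EQ-5D-5L & EQ VAS), the EQ VAS score "is being recorded at all visits, including Baseline. Integer values range from 0 to 100". The planned analysis is a repeated measures ANCOVA to "compare potential differences in trends over the treatment period using treatment and the Baseline VAS value as predictors". No visit effect, time effect, treatment-by-time interaction or trend contrast is named.

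Three other places bear on how this is read:

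- **Time axis.** SAP 7.1.4 has a general rule: "Where deemed necessary, longitudinal analyses will use the observed durations from baseline". It is conditional and is not tied to EQ VAS.
- **Status.** SAP 7.9.3 says of the secondary efficacy analyses apart from time-to-cure: "Other analyses of secondary efficacy variables will be done on a hypothesis-generating basis, i.e. no p-value adjustments will be conducted".
- **Test level.** SAP 7.1.7 sets 0.05 for the other secondary variables, and SAP 7.1.1 makes tests two-sided by default.

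The five EQ-5D dimensions have the same two predictors ("A repeated measures ANCOVA for each dimension will be conducted using treatment and the baseline value as predictors"), but the SAP states no trend aim for them.

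**The concern.** The stated question and the listed model do not match. With treatment and baseline VAS as the only predictors, the treatment coefficient is the baseline-adjusted difference in mean VAS averaged over the post-baseline visits. Its null hypothesis is equal average level, whereas equal trends means no treatment-by-time effect. Using observed days as a time main effect, as SAP 7.1.4 permits, would not close the gap, because a shared time slope does not compare slopes between arms.

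Two misreadings could follow. If one arm is worse early and better later, the differences partly or wholly cancel in the average, and the report could say that trends do not differ. If the arms differ by a constant amount after baseline, a significant treatment effect could be reported as a difference in trends. Neither depends on missing data; both occur even if every subject attends every visit.

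**Working it through.** **The plan's own figure.** The SAP gives no power, SD, correlation or effect size for EQ VAS. Its only design figure is the sample size for CRR_12 (SAP 5.1): 130 subjects, 116 evaluable, 1:1. That figure reproduces. For 0.63 against 0.83, one-sided alpha 0.05 and 80% power, n per arm = (1.645 + 0.842)² × (0.63×0.37 + 0.83×0.17) / 0.20² = 57.8, so 58. Then 58/0.9 = 64.4, so 65 per arm and 130 in total. It is used here only for the arm sizes of 58 and 65.

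**Assumed inputs.** SD 20 points; within-subject correlation ρ from 0.3 to 0.7, compound symmetric; post-baseline visits at Days 7, 14, 21, 30, 60 and 90, all attended; two-sided 0.05. Visits in fact continue every 30 days until resolution, so stopping at Day 90 is a simplification.

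**What the listed model tests.** In balanced compound-symmetric data, its treatment test is equivalent to an ANCOVA of each subject's mean over the k = 6 visits on treatment and baseline. The residual variance of that mean is SD² × [ρ + (1−ρ)/6 − ρ²].

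- ρ = 0.3: 400 × (0.3 + 0.1167 − 0.09) = 130.7. With 58 per arm, SE = √(2×130.7/58) = 2.12.
- ρ = 0.7: 400 × (0.7 + 0.05 − 0.49) = 104.0. With 58 per arm, SE = √(2×104/58) = 1.89.

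**Case 1: trends cross and the differences average to zero over the visits.** The mean difference is 0, so the treatment test rejects at about its nominal 5% however steep the crossing. Simulation gave 5 to 6%, against 99 to 100% for the treatment-by-time test.

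**Case 2: a straight line in days from −8 at Day 7 to +8 at Day 90.** The mean visit day is (7+14+21+30+60+90)/6 = 37, so the mean difference is −8 + 16 × (37−7)/83 = −2.2 points.

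| n per arm | ρ | SE of mean difference | z | Rejection by listed model |
|---|---|---|---|---|
| 58 | 0.3 | 2.12 | 1.04 | 18% |
| 58 | 0.7 | 1.89 | 1.17 | 22% |
| 65 | 0.3 | 2.00 | 1.11 | 20% |
| 65 | 0.7 | 1.79 | 1.24 | 24% |

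These are normal approximations; simulation gave 18 to 23%.

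The treatment-by-day test works on the slope difference, 16/83 = 0.193 points per day. Each subject's slope has variance SD²(1−ρ)/Σ(day−37)², with Σ(day−37)² = 5072. With 58 per arm:

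- ρ = 0.3: SE = √(2×400×0.7/(5072×58)) = 0.0436, z = 4.4, power about 99%.
- ρ = 0.7: SE = √(2×400×0.3/(5072×58)) = 0.0286, z = 6.7, power essentially 100%.

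**Case 3: a difference growing from 0 to 12 points by Day 90.** In simulation the listed model rejects 63 to 78% and the treatment-by-time test 86 to 100%. The loss is moderate because the average also moves.

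**Case 4: parallel trajectories after baseline, constant 8-point gap.** With ρ = 0.5 the residual variance is 133.3; with 58 per arm the SE is 2.14, z = 8/2.14 = 3.7 and power is about 96%. Across the assumed range the listed model rejects 96 to 99%, and the treatment-by-time test 4 to 5%. The listed model has found a difference in level. Nothing in its output separates that from a difference in trends.

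**Different schedule.** Nine visits to Day 180, SD 15 to 20, ρ 0.4 to 0.6 and 58 per arm gave the same picture. Opposite trends crossing at the mean visit day were rejected 4.8 to 5.8% of the time, against about 100% for the slope test. Identical trajectories in both arms were rejected 4.5 to 5.3%, so the listed model keeps its level when nothing differs.

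**The case against.** **The method name may already imply time.** The strongest objection is that a repeated measures ANCOVA usually carries time as a within-subject factor. Treatment and baseline could then be only the between-subject predictors, and some software prints a time-by-treatment test by default. A reader might infer that the plan definitely tests the wrong hypothesis; the text does not establish that. What stands is narrower: the SAP neither names the term nor says which p-value answers the trend question, and an analyst following the listed predictors would test level.

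**A constant gap is not a clean false positive.** A reader might count Case 4 as a 96 to 99% error rate. The arms are randomised, the model adjusts for baseline, and an 8-point gap at every visit from Day 7 means the arms diverged during treatment. That is a real treatment effect. The problem is its label, since the SAP does not define trend.

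**The 5% figure is a limiting case.** It needs the crossing to average about zero. The straight line in Case 2 gives 18 to 23%, which is still poor.

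**The pattern would be visible anyway.** SAP 7.1.1 requires results by visit and treatment group, including mean change from baseline. An early-worse, later-better pattern would appear in those tables, though only descriptively.

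**Expecting a crossing is speculative.** EQ VAS asks about overall health, and the protocol's hypothesis is less toxicity with 0.08% PHMB. The documents do not predict a crossing, and the point does not need one.

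**The EQ-5D dimensions.** A reader might extend the point to them because the predictors are the same. With no trend aim stated there, no mismatch exists.

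**Conclusion.** The concern holds as a mismatch between a stated aim and a listed model, for EQ VAS alone. Fitted with the predictors given, the treatment test is of average post-baseline level. It has little power against crossing trends: about 5% if the differences cancel and 18 to 23% for the line from −8 to +8, against nearly 100% for a treatment-by-time test. A significant result could come from a constant difference.

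The percentages rest on the assumed SD of 20, correlation of 0.3 to 0.7, effect shapes and the Day 90 cut-off. The direction follows from which contrast is tested and does not depend on them. The consequence is small: the analysis is unadjusted and hypothesis-generating, and neither the CRR_12 nor the time-to-cure conclusion is touched.

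**What to change.** For EQ VAS only, amend the sentence in SAP 7.9.3 so that the model contains baseline VAS, treatment, visit and treatment-by-visit (or observed day and treatment-by-day, in line with SAP 7.1.4). State that the interaction is the test of different trends. If the treatment main effect is kept, report it as a difference in average level over the treatment period.

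The cost is one sentence, two model terms and a few degrees of freedom. If the analysis has already been run, label the interaction test as added afterwards and describe the original treatment effect as a difference in average level.
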